## Abbreviations

AUC-ROC	Area under the receiver operating characteristic curve
CT	Computed tomography
ECMO	Extracorporeal membrane oxygenation
ECPR	Extracorporeal cardiopulmonary resuscitation
FAS	Full analysis set
GDPR	General data protection regulation
HR	Hazard ratio
ICU	Intensive care unit
IMU	Intermediate care unit
OR	Odds ratio
PE	Pulmonary embolism
PS	Propensity score
RR	Risk ratio
RV/LV	Right ventricular/left ventricular

## 1 Background

Current international guidelines recommend intravenous thrombolysis for pulmonary embolism with circulatory shock (high-risk PE). Thrombolysis is a highly effective dissolvent of thromboembolic clots followed by fast improvement in the pulmonary obstruction. The treatment has been shown to decrease the combined outcome of mortality and recurrent PE, but also carries a risk of major bleeding of approximately 10%, including 2% rate of intracranial hemorrhage. Additionally, many PE patients have contraindications to thrombolysis. In high-risk PE where IVT is contraindicated or has failed, surgical embolectomy or catheter-directed interventions (CDI) is recommended. The FlowTriever® retrieval/aspiration system is the first mechanical thrombectomy device to receive PE as an indication from the United States Food and Drug administration agency. It combines large-bore aspiration with expanding mesh disks designed to trap and subsequently retract the blood clots from the pulmonary arteries. The FlowTriever® device is gaining widespread use, but non-industry sponsored studies are small with few high-risk patients.

## 2 Study Objective and Hypothesis

The objective of this study is to evaluate catheter-directed intervention with the FlowTriever® device by comparison to contemporary systemic thrombolysis in patients with acute PE.

The hypothesis is that patients treated with the FlowTriever® device will have lower incidence of the primary outcome variable, the composite endpoint death at 30 days and/or severe bleeding (according to GUSTO bleeding criteria) within 7 days after treatment, than patients treated with contemporary thrombolysis.

## 3 Study Design

This is a national multicenter retrospective observational study including patients with acute PE treated between 2021 and 2023 with FlowTriever® in Sweden, to evaluate safety and effects of treatment with the FlowTriever® device. Treated patients will be compared to patients treated with thrombolysis, in the respective hospital during the time period when FlowTriever® has been in use.

Eligible patients will be identified through screening of the relevant clinics/databases at each participating center for:

- Treatment code(s) for thrombolysis and/or pulmonary thrombectomy
- Diagnosis code(s) for pulmonary embolism and/or pulmonary angiography

Data from patients who have been treated for suspected, but not verified, PE may be collected for descriptive purposes but excluded from comparative analyses.

Data will be collected through review of patient records, and subsequently anonymized, organized and analyzed. Collection, handling, and storage of data will be done in accordance with the General Data Protection Regulation (GDPR).

### 3.1 Inclusion/Exclusion Criteria

Eligible patients are all adult patients ( $\geq 18$  years) who have been treated with FlowTriever® or thrombolysis for acute PE verified by computed tomography pulmonary angiography (CTPA) or angiography, during the time period from January 1st of the year when FlowTriever® was introduced at each respective participating center, to the end of 2023.

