## 4 Study Populations

### 4.1 Full Analysis Set

The full analysis set (FAS) will include all patients treated with FlowTriever® and thrombolysis at the included centers during the years 2021, 2022 and 2023.

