## 5.4 Intervention

Following variables related to the intervention of FlowTriever® will be summarized:

- Indication for intervention (e.g. contraindication to thrombolysis, unsuccessful thrombolysis, other indication)
- Contraindication to thrombolysis (none, trauma, surgery, ischemic stroke, hemorrhagic stroke, active bleeding, risk for bleeding, ongoing anticoagulation, other indication)
- Use of Cellsaver/FlowSaver™ or equivalent
- Rescue treatment after intervention (thrombolysis, surgical embolectomy, ECMO)
- ECMO during intervention (yes, no)
- Technical success (yes, no), defined as achievement of desirable catheter positioning, as assessed by the interventionist
- Procedural success (yes, no), defined as technical success with successful extraction of thrombus material in the absence of major complications, as assessed by the interventionist

- Clinical success (yes, no), defined as hemodynamic or respiratory improvement following intervention, including but not limited to: increase in SaO2, reduced FiO2, regress of hypotension/tachycardia/tachypnoea, reduced need for circulatory support.
- Complications during intervention (bleeding, perforation, other complication)
- Other complications (coded by ICD-10 if relevant)

Following variables related to the treatment with thrombolysis will be summarized:

- Dose of thrombolysis
- Duration of infusion of thrombolysis
- Reason for premature discontinuation of thrombolysis (when relevant)
- Contraindication for thrombolysis (if relevant)
- Rescue treatment after thrombolysis (surgical embolectomy, ECMO)

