## 5.6 Confounders and Predictors

The confounders and predictors for the outcomes will be used in propensity scores and adjustments. All variables listed below will be included when building propensity scores. For the adjusted analyses, only the

strongest confounders and predictors will be part of the analyses. The number of confounders/predictors in the adjusted analyses will be based on the number of events available in the studied cohort. The general recommendation is to not have more than 1 variable/10 events in a statistical model. We will calculate the maximum number of variables in our study as N events/10.

The following variables will be investigated whether they are statistically defined confounders, i.e. related to both the intervention and the outcome:

- Contraindication for thrombolysis (8 categories)
- Insufficient previous effect of thrombolysis
- Cardiac arrest before treatment

The following variables will be investigated for their relation to the study outcomes:

- Age
- Sex
- Active cancer
- Invasive ventilation before treatment
- Circulatory instability
- Chronic heart failure
- Chronic pulmonary disease (COPD, asthma, other)
- Respiratory rate >30 beats/min
- Center

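### All treated patients are compared although contraindication to thrombolysis is a reason for FlowTriever, and no planned analysis restricts explicitly to patients without a contraindication

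*SAP*

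**What the plan says.** Eligibility (SAP section 3.1) covers all adults "who have been treated with FlowTriever® or thrombolysis for acute PE verified by computed tomography pulmonary angiography", within a centre-specific calendar window. The full analysis set (section 4.1) "will include all patients treated with FlowTriever® and thrombolysis at the included centers". Neither section requires that a patient could have received either treatment.

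Section 1 describes where catheter treatment belongs: "In high-risk PE where IVT is contraindicated or has failed, surgical embolectomy or catheter-directed interventions (CDI) is recommended". Section 5.4 collects, for FlowTriever patients, "Indication for intervention (e.g. contraindication to thrombolysis, unsuccessful thrombolysis, other indication". It then lists the contraindication itself in named categories that begin with none. For thrombolysis patients the matching item is "Contraindication for thrombolysis (if relevant", with no list.

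Section 5.6 names "Contraindication for thrombolysis (8 categories" and "Insufficient previous effect of thrombolysis" among the variables to be examined as confounders. Every listed variable goes into the propensity score. The adjusted regression takes only the strongest ones, under a cap: "We will calculate the maximum number of variables in our study as N events/10".

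The primary analysis (section 6.5) is logistic regression on the composite of death at 30 days and/or severe GUSTO bleeding within 7 days. Two sensitivity analyses follow: adjustment for the propensity score, and 1:1 matching on it if at least 70% of FlowTriever patients find a match. Section 6.2 adds a caliper, standardized mean differences, and a drop-out analysis of unmatched FlowTriever patients (Table 1.2).

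**The concern.** Section 2 states one hypothesis for everyone treated with FlowTriever: fewer composite events than with thrombolysis. By the SAP's own account, some of those patients were given FlowTriever because thrombolysis was judged unsuitable. In such patients a regression coefficient for treatment rests partly on the model's form rather than on observed comparators. Several of the listed contraindications, such as active bleeding or recent surgery, could plausibly also bear on bleeding or death, the two components of the composite.

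The SAP separates one of the two indications named in section 1. Patients who had thrombolysis before FlowTriever are described on their own, with no formal comparison (section 3.2). Patients with a contraindication get no parallel treatment, and the subgroups in section 6.7 cover only ECMO and cardiac arrest. A reader of Table 4.1 would therefore have no direct view of the result among patients for whom neither treatment was ruled out on record.

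**Working it through.** **Inputs.** From section 6.1: 60 FlowTriever and 200 thrombolysis patients, event rates 20% and 40%, two-sided Fisher's exact test, alpha 0.05, power at least 80%. From section 6.5: the 70% matching condition. From section 5.6: the cap of one variable per 10 events. The contraindicated shares p (FlowTriever) and q (thrombolysis) are not in the SAP; every value used below is an assumption.

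**1. The SAP's own figure.** Enumerating both binomials (60 at 0.20, 200 at 0.40) under Fisher's exact test gives power of 82.7%. The stated minimum of 80% is reproduced, and the point does not depend on any error in the sample size.

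**2. What each planned analysis does about overlap.**

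| Analysis | Uses contraindication? | Limits itself to comparable patients? |
|---|---|---|
| Primary regression (6.5) | If retained as a confounder, under the cap | No |
| Propensity score adjustment (6.5) | Yes, in the score | No |
| 1:1 caliper matching (6.2, 6.5) | Yes, in the score | Yes, on the score, but only if at least 70% match |
| Drop-out analysis (6.2, Table 1.2) | Can describe it | Compares matched with unmatched FlowTriever patients; gives no treatment effect |
| Subgroups (6.7) | No | No |

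The one analysis that enforces overlap is withheld when overlap is poor. The threshold is 0.70 × 60 = 42 matched patients.

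**3. Room in the adjusted model.** Expected events are 60 × 0.20 + 200 × 0.40 = 12 + 80 = 92, so the cap is 92/10 = 9.2, about 9 variables. If the cap counts parameters, eight categories use 7 of them, or 8 if none is a further level, leaving 1 or 2. If it counts named variables, contraindication uses one. Section 5.6 does not say which.

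**4. How overlap depends on the unknown shares.** If patients could be paired only with others of the same contraindication status (yes or no), the largest matchable share would be [(1 − p) × 60 + min(60p, 200q)] / 60.

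| p | q | Calculation | Share |
|---|---|---|---|
| 30% | 5% | (42 + 10)/60 | 87% |
| 40% | 5% | (36 + 10)/60 | 77% |
| 50% | 2% | (30 + 4)/60 | 57% |
| 50% | 5% | (30 + 10)/60 | 67% |
| 50% | 6% | (30 + 12)/60 | 70% |
| 50% | 10% | (30 + 20)/60 | 83% |
| 60% | 5% | (24 + 10)/60 | 57% |

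The results fall on both sides of 70%. The SAP also does not match this way: it matches on the score, so a contraindicated patient can be paired with a non-contraindicated one. The table shows sensitivity to the unknown shares; it is not a forecast or a bound.

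**5. Precision of a restricted analysis.** The test and rates are as in step 1. With p = 50% and q = 5%, 30 FlowTriever and 200 − 10 = 190 thrombolysis patients remain, and power is about 56%. Keeping 200 comparators and varying only p:

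| p | FlowTriever patients left | Power |
|---|---|---|
| 10% | 54 | 78% |
| 20% | 48 | 75% |
| 30% | 42 | 68% |
| 50% | 30 | 56% |
| 70% | 18 | 36% |

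For scale, the planned 1:1 matched analysis, treated as two independent groups at the same rates, has 60% power with 60 pairs and 44% with 42.

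**The case against.** The strongest reply is that the SAP already handles this. Contraindication is in the propensity score without condition, caliper matching restricts to overlap, balance is checked, and unmatched FlowTriever patients are compared with matched ones. All of that is correct, and the plan should be credited for it. It does not remove the gap: the matching is conditional, and neither regression nor score adjustment supplies comparators where there are none.

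Four stronger readings are tempting, and the document does not support them.

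- *Contraindicated FlowTriever patients have almost no valid comparators.* The categories in section 5.4 include bleeding risk, ongoing anticoagulation and other reasons, which may well occur among thrombolysis patients. The SAP also provides for recording contraindications in that group. No counts are given.
- *The matched analysis would be cancelled.* This needs assumed shares and exact matching on contraindication, which is not the SAP's method. Even then, moving q from 5% to 6% at p = 50% reaches the threshold.
- *Residual confounding works against FlowTriever.* That considers contraindication alone. Section 5.6 also lists cardiac arrest before treatment, whose effect on the comparison is unknown here.
- *Contraindications will be under-recorded among thrombolysis patients.* The conditional wording may simply mean where present, and section 5.6 treats the item as one variable for both groups. The wording leaves a blank open to two readings; it does not show that abstraction differs.

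It is also fair to object that a restricted analysis is less precise. That is a reason to label it supportive, and not a reason to omit it.

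**Conclusion.** The point holds as a gap in the sensitivity analyses and in the definition of one variable. Inclusion is unrestricted, contraindication is a named reason for FlowTriever, the primary model has no overlap restriction, the overlap-enforcing analysis is conditional on 70% matching, and no analysis restricts explicitly on contraindication. These statements come directly from the SAP and need no assumed figure.

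The size cannot be fixed from the document. The extent of non-overlap and the net direction of bias depend on shares that the SAP does not give. The 60 may also be smaller in practice, since section 3.2 makes no formal comparison for patients with prior thrombolysis; the calculations use 60 throughout.

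A reader might infer that the claim against thrombolysis should rest wholly on the restricted comparison. That goes too far: with about 56% power at 30 against 190, compared with about 83% at 60 against 200, the trade is debatable, and the planned main analysis can stand with the restricted one beside it.

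**What to change.** 1. **Section 5.4:** record contraindication to thrombolysis in both groups with the same category list, including none, taken from the pre-treatment record. Remove the conditional wording for the thrombolysis group, so that a blank means missing and not absent. The restricted analysis below depends on this.
2. **Section 6.5 and Table 4.1:** add a pre-specified sensitivity analysis of the primary composite, restricted to patients in either group with no recorded contraindication. Label it supportive and report it beside the main result.
3. **Tables:** tabulate contraindication category by treatment group, and describe contraindicated FlowTriever patients separately, as section 3.2 already does for those with prior thrombolysis.

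The main analysis, the eligibility criteria and the confirmatory family stay as they are. The cost is SAP wording, uniform abstraction of a variable already collected from records, one further model and one tabulation. The drawback is lower precision in the restricted analysis, so its estimate and interval should be read alongside the main result, and a non-significant result should not be taken as evidence of no difference.

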## 5.3 Diagnostic, Pre-, Peri- and Post-Intervention Variables

Following diagnostic variables will be collected and described:

- Time between diagnostic radiology and treatment (hours)
- Type of radiology (CT, angiography)
- Clinical presentation of PE (e.g. hypotension, syncope, cardiac arrest) (yes, no)
- Distribution of PE (unilateral, bilateral, saddle)
- Cardiac arrest before treatment (yes, no)
- ROSC before treatment (yes, no)
- Cardiac arrest during treatment (yes, no)
- Cardiac arrest after treatment (yes, no)
- ECMO initiated before treatment (yes, no)
- ECMO initiated during treatment (yes, no)
- ECMO initiated after treatment (yes, no)
- Extracorporeal cardiopulmonary resuscitation (ECPR) (yes, no)

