## 5.5 Outcome Variables

### 5.5.1 Primary Outcome Variable

The primary variable in this study is the composite endpoint death at 30 days and/or severe bleeding (according to GUSTO bleeding criteria) within 7 days after treatment with the FlowTriever® device or contemporary thrombolysis.

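### The SAP does not say that PE must be verified before treatment, so, read literally, patients who die between thrombolysis and imaging leave the comparison

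*SAP*

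**What the plan says.** Section 3.1 makes eligible all adults given either treatment for "acute PE verified by computed tomography pulmonary angiography (CTPA) or angiography". It gives a calendar window, but no order of verification and treatment, and it names no other route to verification.

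Section 3 handles the remainder: "Data from patients who have been treated for suspected, but not verified, PE may be collected for descriptive purposes but excluded from comparative analyses".

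Section 4.1 does not repeat the verification condition: "The full analysis set (FAS) will include all patients treated with FlowTriever® and thrombolysis at the included centers", for the years 2021 to 2023.

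Outcomes run from treatment. Section 5.5.1 defines the primary variable as: "composite endpoint death at 30 days and/or severe bleeding (according to GUSTO bleeding criteria) within 7 days after treatment with the FlowTriever® device". The same windows apply to the thrombolysis group.

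Three other places bear on timing:
- Section 5.3 collects "Time between diagnostic radiology and treatment (hours)", but only to describe it.
- Section 5.3 also collects "Cardiac arrest before treatment (yes, no)" and, separately, return of spontaneous circulation before treatment.
- Section 5.5.2 takes the pre-treatment RV/LV ratio from CT, up to 48 hours before treatment.

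**The concern.** Follow-up starts at treatment, but the condition for entry can be met after treatment. A patient thrombolysed on suspicion who lives long enough to be scanned becomes verified and is counted. One who dies before a scan stays unverified and is not. Entry to the thrombolysis group then depends partly on surviving the treatment under study.

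Such patients appear to be in scope. Section 3 itself foresees treatment on unverified suspicion. The two arrest variables in section 5.3 allow for arrest without return of circulation before treatment, a situation in which earlier imaging is least assured. Arrest before treatment is also a candidate confounder (section 5.6) and part of a subgroup variable (section 6.7).

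The filter is probably unequal between groups. Angiography counts as verification, and a catheter procedure in the pulmonary arteries normally involves it. That is inference; the SAP does not say so.

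Two confirmatory outcomes in section 6.2 are directly exposed: the composite and 30-day death. Severe bleeding is exposed where early deaths involve bleeding. In the Cox analysis, a patient verified after treatment could not have died between treatment and the scan and still be included. Covariate adjustment, propensity-score adjustment and matching cannot restore patients who never enter the data set.

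**Working it through.** **1. Two patients under the literal reading.** Both receive thrombolysis on suspicion.

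| | Patient A | Patient B |
|---|---|---|
| After treatment | survives, then CT shows PE | dies before imaging |
| Section 3.1 | verified, eligible | not verified |
| Section 3 | in the comparison | descriptive only, if collected |
| Section 5.5.1 | event or no event | event |

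All patients lost in this way are events.

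**2. The plan's own figure.** Inputs from section 6.1: 60 FlowTriever patients at 20%, 200 thrombolysis patients at 40%, two-sided Fisher's exact test, alpha 0.05. Exact enumeration gives a power of 82.7%, which agrees with the stated minimum of 80%. The sample-size statement is not in dispute.

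**3. How many events could be lost.** The SAP gives no number treated before imaging, so two assumptions are needed:
- s = share of the 200 thrombolysed before imaging;
- d = share of those who die before any imaging.

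The 200 at 40% contain 80 events. Excluded deaths = 200 × s × d.

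Observed comparator rate = (80 − 200sd) / (200 − 200sd).

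For s = 10% and d = 30%, 6 are excluded and the rate is 74/194 = 38.1%. With FlowTriever held at 20%, the odds are 0.20/0.80 = 0.25. The odds ratio moves from 0.25/(80/120) = 0.375 to 0.25/(74/120) = 0.405.

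| s | d | Excluded | Observed rate | Loss (points) | OR | Fisher power |
|---|---|---|---|---|---|---|
| 5% | 10% | 1 | 39.7% | 0.3 | 0.38 | 81% |
| 10% | 10% | 2 | 39.4% | 0.6 | 0.39 | 80% |
| 10% | 30% | 6 | 38.1% | 1.9 | 0.41 | 75% |
| 10% | 50% | 10 | 36.8% | 3.2 | 0.43 | 68% |
| 20% | 10% | 4 | 38.8% | 1.2 | 0.40 | 77% |
| 20% | 30% | 12 | 36.2% | 3.8 | 0.44 | 64% |
| 20% | 50% | 20 | 33.3% | 6.7 | 0.50 | 48% |

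The planned difference is 20 points.

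**4. Power if verification before treatment is required.** Assume that the comparator rate stays at 40% and FlowTriever has 60 patients at 20%.

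| Thrombolysis patients removed | n left | Fisher power |
|---|---|---|
| 5% | 190 | 82.1% |
| 10% | 180 | 82.3% |
| 20% | 160 | 79.6% |
| 30% | 140 | 78.0% |

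The slight rise from 190 to 180 reflects the discreteness of the exact test.

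**The case against.** **The wording may already exclude these patients.** Section 3.1 speaks of treatment for verified PE, and section 3 of treatment for suspected PE. Both can be read as the state of the diagnosis when treatment was given. On that reading everyone thrombolysed before imaging is out, whether or not they survive, and the selection does not arise. This stands as a possible reading. But the text does not settle it, and several centres reviewing records retrospectively could apply it differently.

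**Imaging usually comes first.** The interval in section 5.3 and the pre-treatment CT in section 5.5.2 both point that way, and the RV/LV difference is a confirmatory outcome. This also stands, and it makes a large share treated before imaging less plausible. Neither variable is an entry condition, however.

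**Eligibility detail may sit in the protocol.** It may. Section 3.1 nevertheless states the criterion without an order in time, and section 4.1 omits verification altogether.

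**A reader might infer that the comparison is biased against FlowTriever overall.** The documents do not support this. FlowTriever patients must survive to reach the procedure, and section 3.2 places patients who received thrombolysis first within the intervention group. That selection works in the opposite direction, and its size is also unknown.

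**A reader might reach a larger loss** by removing a share of all composite events in those treated before imaging. Suppose 20% are treated before imaging with a 70% event risk, the others have 35%, and 50–80% of those events are lost. The rate then falls from 0.8 × 0.35 + 0.2 × 0.70 = 42% to 0.35/0.93 = 37.6% or 0.308/0.888 = 34.7%, a loss of 4.4–7.3 points. But the composite includes patients who bleed severely and survive, and they can be imaged. If 50 of the 70 points are deaths (assumption), the rates are 0.37/0.95 = 38.9% and 0.34/0.92 = 37.0%, a loss of 3.1–5.0 points. Nothing in the SAP supports any of these shares.

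**Conclusion.** The point holds as a gap in the eligibility wording. Read literally, sections 3 and 3.1 let entry to the thrombolysis group depend on surviving to be imaged, and the patients lost are all primary-outcome events. Read as status at treatment, the problem disappears. The SAP should not leave that choice open.

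The size is unknown. With one excluded death the comparator rate moves by 0.3 points. With 10–20% treated before imaging it moves by 0.6 to 6.7 points over d = 10–50%, and by 1.9 to 3.8 points at d = 30%. These figures rest on assumed s and d, a true comparator rate of 40%, and a FlowTriever rate of 20% that the rule does not affect.

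This component lowers the comparator rate. Its sign is clear; the sign of the net bias is not. The remedy is cheap and is worth making before the analysis.

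**What to change.** 1. In section 3.1, state that for the primary comparative analysis PE must have been verified before the start of the index treatment, in both groups. Define that start, including for FlowTriever patients whose verifying angiogram is taken in the same session.
2. Align the full analysis set in section 4.1 with this condition.
3. Report by group how many were imaged only after treatment and how many were never imaged, with the deaths in each.
4. Add a sensitivity analysis of the primary outcome that includes both the patients imaged after treatment and the treated patients never verified. Adding only the former brings back the selected survivors. Collection of the unverified patients in section 3 then has to be firm, not optional.

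This defines an analysis set and implies nothing about how patients should be treated.

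Cost: SAP wording, and record review for the unverified patients. The radiology-to-treatment interval is already collected; it must be recorded so that imaging after treatment can be recognised. The main analysis would have somewhat fewer thrombolysis patients, with exact Fisher power of about 82% at n = 180 and just under 80% at n = 160 if the comparator rate stays at 40%. The main result would apply to patients imaged before treatment. The sensitivity analysis may include some patients who did not have PE, so it shows how far the result could move and does not replace the main estimate.
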